6.3 Basic Definitions

Age

Number of years at time of enrollment as recorded on the electronic case report form.

Investigational Product (IP)

Etanercept (or placebo for etanercept) and methotrexate (or placebo for methotrexate).

Adverse Event

In addition to the International Conference on Harmonisation (ICH) Guidance definition, an adverse event also includes any occurrence or worsening of a pre-existing medical condition.

Treatment-Emergent Adverse Event (TEAE)

TEAE during the run-in period is an adverse event that occurs on or after Run-In Day 1 (as determined by adverse event start date and pre-treatment flag NE 'Y' on the Events CRF) and up to Study Day 1. TEAE during the double-blind period is an adverse event that occurs on or after Study Day 1 (as determined by adverse event start date and pre-treatment flag NE 'Y' on the Events CRF) and up to 30 days after the last dose of IP.

Subject Incidence Rate

The subject incidence rate for a given event in a given time period is defined as the number of subjects with a first reported occurrence of the event divided by the number of subjects who entered the time period. For subjects with multiple occurrences of the same event, the event will only be counted once per subject.

Actual treatment received

Safety analyses will be performed on the Safety Analysis Sets, which analyzes subjects by actual treatment received. Actual treatment is defined below:

Actual Treatment In the Open-Label Run-In Period

• Actual Treatment = Etanercept + Methotrexate
Actual Treatment In the Double-Blind Treatment Period
If a subject receives 
- any active methotrexate and no active etanercept, then his/her actual treatment assignment is methotrexate- any active etanercept and no active methotrexate, then his/her actual treatment assignment is etanercept- any active etanercept and any active methotrexate, then his/her actual treatment assignment is etanercept + methotrexate- no active etanercept and no active methotrexate, then he/she received no actual treatment and will not be included in the safety analysis set
Actual Treatment In the Rescue Therapy Period

• Actual Treatment = Etanercept + Methotrexate

Run-in Failure

The subjects who participate in the run-in period but fulfill *any* of the below criteria are deemed not eligible for randomization and are considered run-in failures.

- SDAI > 3.3 at run-in visit 3
- if female and not at least 2 years postmenopausal or having a history of hysterectomy, bilateral salpingectomy, or bilateral oophorectomy, does *not* have a negative urine pregnancy test at baseline
- has any clinically significant change in the Part 1 eligibility criteria during the run-in period
- SDAI > 3.3 and ≤ 11 on two consecutive visits at least two weeks apart
OR
SDAI > 3.3 and ≤ 11 on two or more separate visits
OR
SDAI > 11 at any time during the run-in period
- Clinically significant laboratory abnormality in run-in which per investigator poses a safety risk, will prevent the subject from completing the study, or will interfere with the interpretation of the study results during the run-in period.

Rescue Therapy

After randomization, if a subject experiences Disease-Worsening as defined in [Section 6.3](#), he/she will initiate rescue treatment with etanercept 50 mg once weekly (QW) plus methotrexate (10 to 25 mg). Those assigned to the etanercept plus

methotrexate arm will continue on the assigned treatments, but are still considered to be on rescue therapy once the open-label rescue etanercept or open-label methotrexate eCRF forms are used. Subjects will receive methotrexate at the same dose that they were receiving at screening.

Original treatment assignments will remain blinded. Dispensing of etanercept plus methotrexate rescue therapy will be managed via the Interactive Voice and Web Response System (IXRS).

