## **9.2 Safety Event Reporting Procedures**

### **9.2.1 Adverse Events**

#### **9.2.1.1 Reporting Procedures for Adverse Events That do not Meet Serious Criteria**

The investigator is responsible for ensuring that all adverse events observed by the investigator or reported by the subject that occur after enrollment through the end of treatment period are reported using the Event CRF.

The investigator must assign the following adverse event attributes:

- Adverse event diagnosis or syndrome(s), if known (if not known, signs or symptoms),
- Dates of onset and resolution (if resolved),
- Severity (and/or toxicity per protocol),
- Assessment of relatedness to investigational product(s), and
- Action taken.

The adverse event grading scale used will be the Common Toxicity Criteria Version 4.0. The grading scale used in this study is described in [Appendix A](#). The investigator must assess whether the adverse event is possibly related to the investigational product(s). This relationship is indicated by a “yes” or “no” response to the question: Is there a reasonable possibility that the event may have been caused by the investigational product(s)?

The investigator is responsible for reviewing laboratory test results and determining whether an abnormal value in an individual study subject represents a clinically significant change from the subject’s baseline values. In general, abnormal laboratory findings without clinical significance (based on the investigator's judgment) are not to be recorded as adverse events. However, laboratory value changes that require treatment or adjustment in current therapy are considered adverse events. Where applicable, clinical sequelae (not the laboratory abnormality) are to be recorded as the adverse event.

The Investigator is expected to follow reported adverse events until stabilization or reversibility.

If the severity of an adverse event changes from the date of onset to the date of resolution, record as a single event with the worst severity on the Adverse Event Summary CRF.

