**3. SERIOUS ADVERSE EVENT**

Provide the date the investigator became aware of this information: Day    Month    Year

Serious Adverse Event diagnosis or syndrome if diagnosis is unknown, enter signs / symptoms and provide diagnosis, when known, in a follow-up report  List one event per line. If event is fatal, enter the cause of death. Entry of "death" is not acceptable, as this is an outcome.	Date Started Day    Month    Year	Date Ended Day    Month    Year	Check only if event occurred before first dose of IP	Is event serious?  Yes  No	Serious, enter Serious Criteria code (see codes below)	Relationship Is there a reasonable possibility that the Event may have been caused by IP or an Amgen device used to administer the IP?						Outcome of Event Resolved Not resolved Fatal Unknown  eg, biopsy	Check only if event is related to study procedure
						Etanercept	Methotrexate	PFS	Device	Other	Unknown		
						No/ Yes/	No/ Yes/	No/ Yes/	No/ Yes/	No/ Yes/			
						No/ Yes/	No/ Yes/	No/ Yes/	No/ Yes/	No/ Yes/			
						No/ Yes/	No/ Yes/	No/ Yes/	No/ Yes/	No/ Yes/			

Serious Criteria: 01 Fatal    02 Immediately life-threatening    03 Required/prolonged hospitalization    04 Persistent or significant disability /incapacity    05 Congenital anomaly / birth defect    06 Other medically important serious event

**4. Was subject hospitalized or was a hospitalization prolonged due to this event?**  No  Yes If yes, please complete all of Section 4

Date Admitted Day    Month    Year	Date Discharged Day    Month    Year

**5. Was IP/drug under study administered/taken prior to this event?**  No  Yes If yes, please complete all of Section 5

IP/Amgen Device:	Date of Initial Dose Day    Month    Year	Prior to, or at time of Event				Action Taken with Product 01 Still being Administered 02 Permanently discontinued 03 Withheld	Lot # and Serial #
		Date of Dose Day    Month    Year	Dose	Route	Frequency		
Etanercept/Prefilled Syringe (PFS)  blinded  open label							Lot # _____  Unknown Serial # _____   Unavailable / Unknown
Methotrexate  blinded  open label							Lot # _____  Unknown Serial # _____   Unavailable / Unknown

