11.6.1 Adverse Events

The Medical Dictionary for Regulatory Activities (MedDRA) version 21.0 or later will be used to code all adverse events (AE) to a system organ class and a preferred term. All adverse events occurring in the Run-In Period will be summarized for the Run-In Period Safety Analysis Set). All adverse events occurring during the double-blind treatment period and 30-day safety follow-up will be summarized for the Post-Run-In Safety Analysis Set. The subject incidence of AEs will be summarized for all treatment-emergent AEs, serious AEs, AEs leading to withdrawal of investigational product, and fatal AEs.

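### A non-serious event that begins in run-in and worsens after Study Day 1 is counted as a run-in TEAE and is missing from the double-blind TEAE incidence

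*SAP*

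**What the plan says.** The plan handles adverse events in three steps.

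- **Recording.** Protocol 9.2.1.1 collects non-serious events from enrollment to the end of treatment. Each event carries "Dates of onset and resolution (if resolved"), severity, relatedness and action taken. If severity changes between onset and resolution, the site is to "record as a single event with the worst severity on the Adverse Event Summary CRF".
- **Allocation to period.** SAP 6.3 gives two parallel rules. For run-in: "TEAE during the run-in period is an adverse event that occurs on or after Run-In Day 1 (as determined by adverse event start date"), with an upper limit of Study Day 1. For the double-blind period: "TEAE during the double-blind period is an adverse event that occurs on or after Study Day 1 (as determined by adverse event start date"), with an upper limit of 30 days after the last dose. Both also require that the pre-treatment flag is not set. Actual treatment in run-in is etanercept plus methotrexate for everyone.
- **Tabulation.** SAP 11.6.1 summarizes the periods separately: "All adverse events occurring in the Run-In Period will be summarized for the Run-In Period Safety Analysis Set" and "All adverse events occurring during the double-blind treatment period and 30-day safety follow-up will be summarized for the Post-Run-In Safety Analysis Set". The categories are TEAEs, serious events, events leading to product withdrawal, and fatal events.

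SAP 6.3 also states that "an adverse event also includes any occurrence or worsening of a pre-existing medical condition". SAP section 12, which lists changes from the protocol, adds no rule for an event that starts in one period and worsens in the next.

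**The concern.** Every subject has 24 weeks of open-label combination treatment, with event collection, before randomization. Some events will therefore be ongoing at Study Day 1. What happens to them afterwards is a post-randomization outcome, and it may differ between groups because the groups differ in which drug is withdrawn.

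Under the rules above, such an event is placed by when it began, not by when it got worse. A worsening on randomized treatment is then credited to a period with one common treatment and no comparison, and is lost from the comparison of TEAE incidence between groups. The single record also does not show when the worst grade was reached, so the analysis cannot recover the information later.

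**Working it through.** The plan states no figure on this point, so there is none to reproduce. The check applies the SAP 6.3 rule to example records, with days numbered from Study Day 1 = 1.

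**Rule as coded.** Run-in if Run-In Day 1 ≤ start ≤ Study Day 1. Double-blind if Study Day 1 ≤ start ≤ last dose + 30 days. The flag is taken as not set.

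| Record | Start date used | Period |
|---|---|---|
| Onset Day −20, mild; grade 3 on Day 60 | Day −20 (Protocol 9.2.1.1 keeps one record) | Run-in only |
| Onset Day −20; serious on Day 60 | Day −20 if kept as one record | Run-in only |
| Onset Day −20; product withdrawn on Day 60 | Day −20 if kept as one record | Run-in only |
| New onset Day 60 | Day 60 | Double-blind |
| Onset on Study Day 1 | Day 1 | Both |

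1. *Row 1* follows directly from the text. The recording rule forbids a new record for a change in severity, and the allocation rule looks only at the start date.
2. *Rows 2 and 3* hold only if no new record is opened. The protocol does not settle this. The contingency form in Protocol Appendix B says "List one event per line" and puts start date and seriousness on that line, which points to one record. No instruction says what to do when an ongoing event becomes serious. If a new record dated Day 60 were opened, both rows would move to the double-blind period.
3. *Row 5* arises because the upper limit of the run-in rule can be read as including Study Day 1, where the double-blind rule begins.
4. *Partial dates.* SAP 10.3.4 sets an incomplete start date to Study Day 1 when the known part matches Study Day 1 and the event stopped later. That moves some run-in onsets the other way, into the double-blind period.

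**Size, on assumed inputs.** Let *a* be the share of subjects with an event ongoing at Study Day 1 and *w* the share of those whose event then worsens. Neither is in the documents. Subjects affected = *N* × *a* × *w*.

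| *a* | *w* | Per 100-subject arm | Of 250 randomized |
|---|---|---|---|
| 0.10 | 0.02 | 100 × 0.002 = 0.2 | 250 × 0.002 = 0.5 |
| 0.20 | 0.10 | 100 × 0.02 = 2.0 | 250 × 0.02 = 5.0 |
| 0.30 | 0.20 | 100 × 0.06 = 6.0 | 250 × 0.06 = 15.0 |

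**The case against.** The case on the other side is substantial and narrows the point.

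- **Serious events and withdrawals.** A reader might infer that these too are certainly filed to run-in. The single-record instruction concerns severity only and sits in the section on non-serious events. Protocol 9.2.2, on serious events, has no such instruction. SAP 11.6.1 does not repeat the start-date rule for the serious, withdrawal and fatal summaries; it refers only to events occurring in the period. This is ambiguity, not exclusion.
- **Missing from every double-blind table.** That does not follow either. SAP 11.2 reports reasons for discontinuation by randomized group, and SAP 10.4 summarizes reasons for early withdrawal. Protocol 10.5.5 plans shift tables of worst laboratory toxicity by treatment group. SAP 11.6.2 makes those tables optional but commits to listings of grade 3 and 4 values. Event tables are thus not the only randomized safety evidence.
- **Severity shown in the wrong table.** No adverse event table by grade is planned, so the run-in summary would not display a grade reached on blinded treatment.
- **Contradiction with the adverse event definition.** Worsening of a pre-existing condition can be an event in its own right, with its own start date. The definition and the TEAE rule can coexist. What is missing is a statement of how a worsening run-in event is entered. CRF completion guidance might supply it, but is not among the documents.
- **Low rates.** Subjects have had at least 6 months on both drugs before run-in (criteria 107 and 108). Criteria 227 and 229 remove those with clinically significant changes or laboratory concerns before randomization. No arm starts a new active drug at randomization. Worsening of the arthritis itself is captured by the SDAI endpoints.

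These arguments limit the scope and suggest a small number. They do not remove the gap for a non-serious event whose severity rises after Study Day 1: the protocol forbids a new record, and the SAP then assigns the event to run-in.

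**Conclusion.** The point holds in limited form. For non-serious events with run-in onset and a later increase in severity, following both documents as written removes the worsening from the double-blind TEAE incidence. For events that later become serious or lead to product withdrawal, the documents do not determine the period, and two programmers could produce different tables. The adverse event definition is unreconciled with the start-date rule rather than in conflict with it.

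The size is unknown. The 0.5 to 15 of 250 rests entirely on the assumed shares in the table, and the eligibility rules argue for the lower part. The effect is confined to safety reporting. It should still be corrected, because it determines which events enter the randomized safety comparison and the remedy is simple.

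**What to change.** - **SAP 6.3.** Define a double-blind TEAE as an event that starts, increases in severity or becomes serious on or after Study Day 1, keeping the existing upper limit.
- **SAP 11.6.1.** Tabulate serious events and events leading to product withdrawal by the date of that outcome, not by onset.
- **Protocol 9.2.1.1.** When an event ongoing at randomization increases in severity, require either a dated severity change or a new record. Without a date, the revised SAP definition cannot be applied.
- **Study Day 1.** Assign onsets on that day to one period only and use the same boundary in both rules.
- **If data collection is too advanced** for the protocol change, list by treatment group all events with run-in onset that were ongoing at Study Day 1, with worst severity, seriousness and action taken. The SAP is dated 7 January 2020, so this may be the practical route.

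The cost is a little extra data entry for events ongoing at randomization, a few sentences in the SAP and, for 9.2.1.1, a protocol amendment with the ethics approval that Protocol 12.1 requires. The fallback listing needs no amendment.

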6.1 Study Time Points

Enrollment Date

A subject's Enrollment Date is defined as the date he or she has met all Part 1 eligibility criteria and the enrollment call in the IXRS system has been completed.

Part 1/Run-in Period

The 24-week period after enrollment and prior to randomization. Specifically, the period begins when a subject initiates treatment with open-label run-in etanercept and/or open-label run-in methotrexate per the eCRF at the same dose he or she was receiving at screening. There are three visits associated with the Run-in Period: Run-in Visit 1, Run-in Visit 2, and Run-in Visit 3.

Run-In Day 1

A subject's Run-In Day 1 is defined as the date of the first dose of IP administration during Part 1.

Run-In Day

A subject's Run-In Day = (Visit Date – Run-In Day 1 date) + 1.

Run-In Failure Date

A subject's Run-In Failure Date is the date the subject ended run-in due to protocol specified criteria per the eCRF.

Randomization Failure Date

A subject's Randomization Failure Date is the date the subject ended run-in due to any reason and was not randomized.

End-of Run-In Date

A subject's End-of Run-In Date is the date subject ends the run-in period per the CRF.

Randomization Date

A subject's Randomization Date is the date when a randomization number is assigned to him or her through the Interactive Voice/Web Response System (IXRS).

Study Day 1

A subject's Study Day 1 is defined as the date of the first dose of IP administration after randomization, or the randomization date if the subject is not dosed.

Baseline

The last measurement for the endpoint of interest taken on or prior to Study Day 1 and after Run-In Visit 3. Hematology and chemistry profiles were not assessed on Day 1; their Run-in Visit 3 values will be used when reporting baseline.

Baseline for Concomitant Medications

Run-In Period Baseline for Concomitant Medications is enrollment date, and Post-Run-In Period Baseline for Concomitant Medications is randomization date.

Study Day

For a given study visit, the study day for a subject is defined as:

Study Day = (Visit Date – Study Day 1 date) + 1.

Part 2/Treatment Period

The up-to 48-week double-blind period beginning with Study Day 1 and ending with the End of Study date.

SDAI Assessment Datea

The SDAI Assessment Date is the latest date of the assessments for Tender Joint Count, Swollen Joint Count, Physician Global Assessment, Patient Global Assessment, and CRP for a given SDAI score.

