Disease-Worsening Date (DW Date)

A subject's Disease-Worsening Date is the first Visit Date in which the subject meets the definition for Disease-Worsening. With the exception of analysis using multiple imputation method, Disease-Worsening classification is based on observed SDAI values only. Each subject will have at most one DW Date. A subject's disease-worsening date is used to define his/her Disease-Worsening Baseline.

Rescue Date

A subject's rescue date is the Visit Date in which he or she first receives rescue therapy as identified by the Investigational Product Administration (Rescue Therapy Etanercept) or Investigational Product Administration (Rescue Therapy Methotrexate) form.

Rescue Therapy Period

For the Rescue Analysis Set as defined in [Section 7.4](#), the Rescue Therapy Period begins with the Rescue Date through the EOS Date.

Disease-Worsening Analysis Visit (DW_visit)

The DW_visit defines the analysis visit after a subject fulfills disease-worsening criteria. Details of DW_visit derivation are in [Appendix A](#).

Rescue Analysis Visit (Rescue_visit)

Rescue_visits define the analysis visits after a subject initiates rescue therapy. Details of Rescue_Visit derivation are in [Appendix A](#).

End of Treatment (EOT)

The End of Treatment for a subject is the subject's last assessment for the protocol-specified treatment phase of the study.

End of Study Date

The End of Study Date for a subject is the date the subject completes the safety follow-up phone call, or the date of the Early Termination (ET) visit if no safety follow-up phone call is completed. The date the subject has ended the study is recorded on the End of Study Electronic Case Report Form (eCRF).

End of Study

The End of Study is the date when the last subject across all sites is assessed or receives an intervention for evaluation in the study (ie, last subject last visit).

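### SAP 6.3 gives rescue its own actual-treatment label, but no safety window, denominator or adverse-event table is cut at rescue, so a literal reading moves pre-rescue events into the combination column

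*SAP*

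**What the plan says.** SAP 6.3 (Actual treatment received) has three blocks: run-in, double-blind and rescue.

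- **Double-blind block.** A subject with "any active etanercept and any active methotrexate, then his/her actual treatment assignment is etanercept + methotrexate". The rule is written per subject and carries no date limit.
- **Rescue block.** It is headed "Actual Treatment In the Rescue Therapy Period" and assigns etanercept + methotrexate.

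SAP 6.1 sets the periods. The Treatment Period is the "double-blind period beginning with Study Day 1 and ending with the End of Study date". For the Rescue Analysis Set, "the Rescue Therapy Period begins with the Rescue Date through the EOS Date". A subject's "rescue date is the Visit Date in which he or she first receives rescue therapy", and a record on either the rescue etanercept form or the rescue methotrexate form is enough to set it. The Rescue Analysis Set in SAP 7.4 requires an active rescue dose of both products.

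For adverse events, "TEAE during the double-blind period is an adverse event that occurs on or after Study Day 1", and the window closes 30 days after the final dose of investigational product. SAP 6.3 defines treatment-emergent events for the run-in and double-blind periods only. Incidence is tied to a period: "The subject incidence rate for a given event in a given time period is defined as the number of subjects" with a first event, divided by those who entered that period.

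SAP 11.6 uses two safety sets, one for run-in and one for everything after it. SAP 11.6.1 plans one post-randomization event summary, covering the double-blind period and the 30-day follow-up. SAP 11.6.2 groups its optional grade 3 or higher laboratory summary by treatment received over the study. SAP 11.6.4 gives exposure by treatment group without separating rescue doses.

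**The concern.** The rescue regimen contains both active drugs. A subject randomized to methotrexate alone or etanercept alone who is rescued therefore meets the both-actives rule at some point inside the Treatment Period as SAP 6.1 defines it. If the label is then fixed for the subject, events that began on monotherapy are reported as combination events, and the subject leaves the monotherapy denominator.

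Rescue follows disease worsening, so the subjects who change column are selected by outcome. On the planning remission rates, more of them would be expected to come from the methotrexate arm. Both protocol and SAP state a safety objective, and these tables are where a reader would compare the three regimens. Two programmers working from the same SAP could produce different event tables.

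**Working it through.** **1. The periods.** The Treatment Period runs from Study Day 1 to the End of Study date. The Rescue Therapy Period runs from the Rescue Date to the same end point. The second lies wholly inside the first, so an active rescue dose is also an active dose received in the Treatment Period.

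**2. The event window.** Rescue doses are recorded on forms that SAP 6.1 names as investigational-product administration forms. A window that closes 30 days after the final product dose therefore naturally runs on through rescue. No rescue-period window exists.

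**3. One subject under each reading.** Take a methotrexate-arm subject with event A before rescue and event B after it, having received both rescue products.

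| Reading | Event A | Event B | Denominator |
|---|---|---|---|
| Literal: any active product to End of Study | combination | combination | combination only |
| By period: label changes at rescue | methotrexate | combination | methotrexate, then not stated |

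The readings differ on event A and on the denominators. Event B carries the combination label under both. Under the by-period reading, the SAP does not say whether event B joins the combination-arm column or a separate display, nor which denominator applies. A rescued combination-arm subject keeps the same label either way.

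**4. The planning figures.** SAP 3.2 gives response rates of 50% (methotrexate) and 72% (etanercept), with 100 per monotherapy arm, 50 on combination, a two-sided 0.05 test and 90% power. These reproduce: the two-proportion formula gives 102 per arm with pooled variance and 99 with unpooled variance, and 100 per arm gives 89.7% power. Enrollment is 250/0.70 = 357.1, rounded up to 358.

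**5. Size under the literal reading.** The documents give no rescue rate. Assume that a common share f of planned Week 48 non-responders is rescued with both products.

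- Planned non-responders: methotrexate 100 × (1 − 0.50) = 50; etanercept 100 × (1 − 0.72) = 28; total 78.
- Etanercept column = 100 − 28f. Methotrexate column = 100 − 50f. Combination column = 50 + 78f.

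| f | Etanercept | Methotrexate | Combination | Share of combination column randomized to monotherapy |
|---|---|---|---|---|
| 0 | 100 | 100 | 50 | 0% |
| 0.25 | 93 | 87.5 | 69.5 | 19.5/69.5 = 28% |
| 0.50 | 86 | 75 | 89 | 39/89 = 44% |

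At any common f, the methotrexate column loses 50/28 = 1.8 times as many subjects as the etanercept column.

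**The case against.** The strongest reply is that the SAP already separates the periods. SAP 6.3 has a rescue block, SAP 11.6 imports that section by reference, incidence is defined per period, and rescue doses have their own forms. On this view the literal reading would make the rescue block pointless for rescued monotherapy subjects. The nesting of periods also follows from the design, since the protocol places rescue inside the double-blind period.

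Much of this stands. A reader might infer that the SAP forces a choice between two wrong results: pre-rescue events moved to combination, or rescue-time events counted under monotherapy. The documents do not support that. The by-period reading is available, and the rescue block contradicts the second result for anyone in the Rescue Analysis Set. But the block supplies only a label. No event window, denominator or table uses it, and SAP 12 created a separate run-in safety set without a rescue counterpart.

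A reader might also infer that laboratory samples from the rescue visit are wrongly attributed because the Rescue Date is a visit date. Protocol 7.2.6 and 7.4 largely settle this: product is given after the other procedures, and blood is drawn before dosing. What remains is a convention for events around the first rescue dose, some of which may be taken at home.

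Finally, limiting the Rescue Therapy Period to subjects with both rescue products has a purpose. A Rescue Date needs only one form. Giving everyone with a Rescue Date the combination label would misclassify, for example, a methotrexate-arm subject with only rescue methotrexate recorded.

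**Conclusion.** The point holds as an inconsistency in the safety definitions. The label is split by period, while the Treatment Period, the double-blind event window and the event summary are not. Applied as written, the both-actives rule attributes a rescued monotherapy subject's earlier events to the combination.

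The column counts are illustrative. They assume 25% to 50% of planned non-responders rescued, the same share in both arms, and the literal reading. Non-responders also include dropouts and subjects out of remission at Week 48 who never met the worsening criteria, so treating all 78 as rescued would not be a realistic case. The planning rates make more rescue on methotrexate likely but do not establish it.

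A reader might infer that the trial's main conclusion is at risk. It is not: the safety tables are descriptive, and primary efficacy is analyzed as randomized, with disease worsening counted as non-response. The point should be fixed before the safety tables are programmed.

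**What to change.** In SAP 6.1, 6.3 and 11.6:

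1. Base the double-blind actual-treatment label only on product received before the first rescue dose.
2. End the double-blind event window, and the data used in any laboratory tables, at the earlier of the first rescue dose and 30 days after the final product dose. State a convention for events starting on the day of the first rescue dose. Counting them as rescue-period events would mirror the existing Study Day 1 rule.
3. Show later events in a separate rescue-period table whose denominator is the subjects who received any rescue dose. Label it by the active products actually received, so that a subject with one rescue product recorded is not automatically etanercept + methotrexate. A breakdown by original arm is an optional supplement.
4. State where combination-arm subjects appear. SAP 6.3 says they are "still considered to be on rescue therapy once the open-label rescue etanercept or open-label methotrexate eCRF forms are used", so they belong in the rescue-period table from their first rescue dose.

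The cost is SAP wording and one further set of event tables, plus laboratory tables if they are produced. Dose dates and event onset dates are already collected, and no visit or treatment changes. The drawback is that events soon after rescue may still reflect the earlier monotherapy. The cut is a convention, and the SAP should say so.
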